Methodology: This Phase 2, multi-center, randomized, double-blind, placebo-controlled trial will assess the safety and efficacy of allogeneic cardiosphere-derived cells (CDCs), or CAP-1002, administered as four IV infusions, one every three months, for the treatment of subjects with DMD. Subjects with a clinical diagnosis of DMD confirmed by genetic testing and evidence of skeletal muscle impairment will undergo a battery of tests and procedures during a 30-day screening period to determine eligibility based on protocol inclusion and exclusion criteria. Eligible subjects will be prospectively randomized in stratified permuted blocks to CAP-1002 or placebo (1:1 ratio). To allow sufficient time for delivery of Investigational Product (IP), subjects must be randomized approximately 7 days in advance of their first IV infusion of Investigational Product (IP) on Day 1. Randomization will be stratified by site and entry item score of the Performance of the Upper Limb 1.2 (PUL). Subjects will undergo baseline safety and efficacy assessments (Table 3) prior to the first infusion of IP (CAP-1002 or placebo). Administration of IP (Day 1) should occur within a maximum of 14 days following randomization; if a delay of more than 14 days between randomization and IP administration is unavoidable, a conversation between the Investigator and Medical Monitor should occur to determine the need for repeat assessments prior to infusion. Subjects who are not randomized may be re-screened at the discretion of the Investigator.	

Subjects will complete study assessments at Screening; Baseline (≤ 2 days prior to Day 1); Day 1; Weeks 4 and 6 (± 7 days, each); Month 3 (± 14 days), Month 4.5 (± 14 days), and Months 6, 9, and 12 (± 14 days, each).

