⁵ A blood sample for tryptase should be obtained within 3 hours of the onset of allergic signs or symptoms, and a second red top tube should be drawn within 3 hours of a severe allergic reaction, and frozen at -20°C, for other future analyses.

⁶ All IP infusions will be conducted in an outpatient setting at the investigative site. Prior to each IP infusion, medications will be administered to the subject as determined by the Investigator based on the pre-treatment guidelines provided by Capricor and/or institutional protocols to minimize the risk of potential severe allergic reactions such as anaphylaxis. Subjects will be observed for at least 2 hours post infusion, including pulse oximetry monitoring for at least 30 minutes post infusion. Sites will observe local institutional policies related to parenteral infusions and post-infusion monitoring.

⁷ A safety phone call will be performed 14 days (± 3 days) after each IP infusion, and if clinically indicated, an unscheduled in-person visit will be performed at the investigative site with targeted assessments based on presentation of signs and symptoms.

⁸ Ulna length will be measured in all subjects. Standing height will be measured if a subject is capable. If standing height cannot be measured, height will be calculated using a measurement of ulna length per Section 13.1.2.

⁹ Paired forced-maneuver testing will be performed on Screening Day 1 and Day 2 (approximately 24 hours between testing sessions) to confirm acceptable FVC variance (exclusion criterion 7). PFT testing sequence: SVC, forced maneuver (FEV₁/FVC/PEF), MIP, MEP, PCF, and IFR.

¹⁰ Blood collections for clinical laboratory and DSA testing at Week 4 and pre-dose DSA testing at Months 3, 6, and 9 will occur either at the investigative site or remotely at a designated central laboratory patient service center.

¹¹ Blood and urine samples will be collected using trial-specific laboratory kits, and then shipped to and tested at a central laboratory. Required sample collection for a visit may occur on multiple days; if the visit includes an IP infusion, sample collections should occur prior to IP administration. Baseline blood samples may be collected on Day 1 prior to IP administration to reduce number of venipunctures.

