10.6. Discontinuation of Medications Prior to Infusion

If clinically acceptable in the judgement of the Investigator, beta blockers and angiotensin-converting enzyme inhibitors (ACEi) should not be administered on the day of infusion. Furthermore, since all subjects who are pre-treated with glucocorticoids, as determined by the site PI as part of their pre-medications, will likely start pre-treatment with glucocorticoids beginning 12 – 14 hours prior to infusion (see Section 21.2), their standing steroid medications schedule may need to be adjusted. Specifically, standing glucocorticoids should not be administered in the setting of glucocorticoid pre-treatment within 24 hours prior to the time of scheduled infusion or on the day of the IP infusion.

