10.7. Administration

All investigational product (IP; CAP-1002 or placebo) delivery will be conducted in an outpatient setting at the investigative site on Day 1 and Months 3, 6, and 9. Subjects must complete all other trial assessments prior to IP infusion, excluding those related to the IP infusion (e.g., post-infusion

monitoring).

Prior to each infusion, it is recommended that site personnel meet to discuss the logistics for that specific infusion.

Capricor requires that subjects be treated prior to each IP infusion with medications to minimize the risk of potential severe allergic reaction. It is strongly encouraged that pre-medication be administered according to the guidelines in Section 21.2, however, investigative sites may use institutional protocols established for anaphylaxis prevention should they be at least physiologically comparable to the guidelines in Section 21.2.

[REDACTED]

[REDACTED]

[REDACTED]

[REDACTED]

[REDACTED]

[REDACTED]

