21. APPENDICES

21.1. Appendix I: Exon 44-Skip Amenable Dystrophin Mutations

Deletions to the following exons of the dystrophin gene are amenable to exon-44 skipping ([den Dunnen J.T., 2014](#); [White and den Dunnen, 2006](#); [Aartsma-Rus et al., 2006](#); [Aartsma-Rus, 2014](#)):

10-43	24-43	34-43	45
11-43	25-43	35-43	45-54
13-43	26-43	36-43	45-56
14-43	27-43	37-43	45-62
15-43	28-43	38-43	
16-43	29-43	39-43	
17-43	30-43	40-43	
19-43	31-43	41-43	
21-43	32-43	42-43	
23-43	33-43	43	

21.2. Appendix II: Pre-Infusion Guidance for Minimizing Risk of Potential Severe Hypersensitivity Reaction

As discussed in Section 10.6, Capricor requires treatment of all subjects prior to each IP infusion to minimize the risk of a potential severe allergic reaction. It is strongly encouraged that pre-medication be administered according to the guidelines in [Table 6](#) including the administration of high dose steroids, H1 and H2 blockers; however, investigative sites may use institutional protocols established for anaphylaxis prevention should they be at least physiologically comparable to the guidelines below.

Final decisions regarding the medication(s), dose(s) administered, and route(s) of administration are to be determined by the Investigator taking into consideration the subject's medical history. For any pre-treatment medication administered, the FDA approved label should be reviewed for information on potential side effects and/or drug interactions and followed for detailed instructions on weight-based dosing.

Of note, for subjects routinely treated with beta blocker and ACEi, the doses of both should be held on the day of infusion, if clinically acceptable in the judgment of the site Investigator. Furthermore, it is recommended that the standing steroid doses should be held if the planned schedule is within 24 hours of the time of scheduled infusion of IP. This is because glucocorticoids will likely be administered as part of the pre-medications beginning 12 – 14 hours prior to infusion of IP.

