4.2 Study Day

The day of first IP administration is defined as Day 1. All other study days will be labeled relative to Day 1. Thus, study day for a particular event date on or after Day 1 is calculated as: $(Date\ of\ event - Date\ of\ first\ IP\ administration + 1)$. An event that occurs prior to Day 1 is calculated as: $(Date\ of\ event - Date\ of\ IP\ administration)$.

The duration of an event will be calculated as $(Event\ end\ date - Event\ start\ date + 1)$. Day 0 will not be used.

The baseline value for each subject is the last non-missing value obtained prior to the time of the first IP administration on Day 1.

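### Baseline blood may be drawn before or after steroid premedication starts, and the SAP treats both as one baseline for laboratory (and possibly biomarker) change from baseline

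*Protocol*

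**What the plan says.** **Timing of the baseline draw.** The Protocol Synopsis sets the visit as "Baseline (≤ 2 days prior to Day 1". Footnote 11 of Table 3 adds: "Baseline blood samples may be collected on Day 1 prior to IP administration to reduce number of venipunctures". The only limit on a Day 1 draw is that it precedes the investigational product (IP). Premedication is not mentioned.

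**Premedication.** Protocol Section 10.7 states: "Capricor requires that subjects be treated prior to each IP infusion with medications to minimize the risk of potential severe allergic reaction". IP means CAP-1002 or placebo, so this applies to both arms. Appendix II (Section 21.2) encourages a regimen "including the administration of high dose steroids, H1 and H2 blockers", and physiologically comparable institutional protocols are allowed. Section 10.6 says that subjects pre-treated with glucocorticoids "will likely start pre-treatment with glucocorticoids beginning 12 – 14 hours prior to infusion", and Appendix II repeats the same lead time. Section 10.6 also says "standing glucocorticoids should not be administered in the setting of glucocorticoid pre-treatment within 24 hours prior to the time of scheduled infusion".

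**Baseline in the analysis.** SAP 4.2: "The baseline value for each subject is the last non-missing value obtained prior to the time of the first IP administration on Day 1".

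**Where it is used.** SAP 7.3 summarizes hematology and chemistry change from baseline at each visit. SAP v3.0 (6.3.9 and Section 8) only lists biomarkers. The post-hoc Addendum (2.6) then analyzes CK isoenzymes with the primary MMRM and the percentile-ranked model, and the other biomarkers with the ranked model only.

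**The concern.** Two subjects with the same underlying laboratory state can have baselines taken under different conditions: one on the usual steroid regimen, the other some hours after premedication, with the standing dose withheld. Nothing visible in the protocol or SAP records which condition applied, separates the two, or adjusts for them. If premedication moves an analyte, part of the reported change from baseline reflects the day of the draw rather than the course of the subject. The same can happen at the other end of the comparison, because Months 3, 6 and 9 are infusion visits and Month 12 is not.

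**Working it through.** The plan gives no figure for this point, so there is nothing to reproduce. The check sets the provisions side by side and then sizes the effect under stated assumptions.

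**1. Does a Day 1 draw follow the steroid start?** Infusions are outpatient, and Table 3 footnote 1 places blood collection (step 9) shortly before infusion (step 11). As an illustration, an infusion at 10:00 on Day 1 puts a start 12–14 hours earlier at 20:00–22:00 the evening before. A blood draw at the site on Day 1 then follows it, while a draw in clinic hours one or two days before Day 1 precedes it. Where both samples exist, SAP 4.2 selects the later one.

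**2. Which rows does footnote 11 cover?** In Table 3:
- Serum chemistry and hematology carry footnote 11 directly.
- Biomarkers carry 16 and 17, and exploratory biomarkers 16 and 18. Neither carries 11.
- The last sentence of footnote 11 speaks of baseline blood samples in general. Creatinine is in both the chemistry and biomarker lists, and SAP 7.3 displays CK isoenzymes as chemistry.

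The allowance is therefore clear for hematology and chemistry, and a matter of interpretation for most biomarkers.

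**3. Which later samples are affected?** Months 3, 6 and 9 are infusion visits. Samples should be taken before IP, possibly over several days, and their timing relative to premedication is not fixed. Week 4, Week 6, Month 4.5 and Month 12 have no infusion that day.

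**4. Size.** Assumptions, none of them in the documents:
- *q*, the share of baselines drawn after premedication starts: 0.25–0.5.
- *d*, the shift that premedication causes in a marker, in SD units: 0.25–1.0.
- A 10/10 split of the 20 subjects.

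*Within-arm change to a visit without premedication (such as Month 12).* The mean shifts by q × d in absolute size: 0.25 × 0.25 = 0.06 SD up to 0.5 × 1.0 = 0.50 SD.

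*Within-arm change to an infusion visit.* If a share *r* of samples at that visit follows premedication, the mean shifts by (r − q) × d. It is zero when r = q. With r = 1 and q = 0.25 it is 0.75 × d, or 0.19–0.75 SD.

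*Noise.* Baseline variance is multiplied by 1 + q(1 − q)d²: from 1 + 0.1875 × 0.0625 = 1.01 to 1 + 0.25 × 1 = 1.25.

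*Chance imbalance.* If K of the 20 subjects have a post-premedication baseline, the number in one arm is hypergeometric:

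| K | P(arms differ by 3 or more subjects) | P(arms differ by 4 or more) |
|---|---|---|
| 5 | 30% | 3% |
| 8 | 17% | 17% |
| 10 | 18% | 18% |

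For K = 8 the difference is always even, so both columns equal 2 × (45 + 1,200 + 9,450)/125,970 = 0.170.

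*Effect of such an imbalance.* A difference of 4 subjects out of 10 shifts an unadjusted between-arm difference in change by 0.4 × d = 0.10–0.40 SD. In a model with baseline as covariate, this is multiplied by the slope of the later value on baseline, so it is smaller when that slope is below 1.

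**The case against.** The case on the other side is substantial, and most of it limits the point rather than removing it.

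- **No systematic bias between arms.** Premedication is required in both arms of a randomized, blinded trial, so the expected shift in the treatment contrast is zero. This stands. A reader might infer that the treatment comparison is biased, and the documents do not support that. If draw day follows site habit, randomization by site and the site term in the model reduce the imbalance further than the table shows.
- **Premedication with steroids is not certain.** It is worded as likely and is decided at the site, institutional alternatives are allowed, and the guideline table is not visible. This stands. It would be wrong to say that every Day 1 draw follows a steroid dose. Varied practice does, however, leave the baselines mixed.
- **All subjects already take steroids.** Inclusion criterion 8 requires at least 12 months of systemic glucocorticoid. The contrast is background treatment against premedication, not steroid-free against steroid. Whether and how far this moves any analyte is not in the documents.
- **Safety endpoints.** A reader might infer that a premedicated white-cell baseline hides leukocytosis in the hypersensitivity or immune sensitization endpoints. Protocol 7.2.1 names leukocytosis as an example sign, not as a change from baseline, and the Clinical Events Committee adjudicates from source documents. The definitions are unaffected.
- **A premedication-free baseline is not plainly better.** It could match Months 3, 6 and 9 less well. A Screening substitute could be about 44 days old (30 days before randomization plus 14 to infusion). This stands, and it argues against redefining the baseline.
- **Nothing shows that mixed draws occurred.** True: the documents permit them and do not say how often they happened.

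**Conclusion.** The point holds in a limited form. For hematology and serum chemistry, the protocol permits baseline draws on either side of the premedication start, and SAP 4.2 does not distinguish them. For biomarkers this depends on how footnote 11 is read, and the footnote marks need to be reconciled with its general wording. The consequences are added noise, possible chance imbalance at n = 20, and within-arm changes that mix two states. On the assumed ranges these are moderate for single analytes and could be negligible if premedication has little effect beyond background steroids. They reach only descriptive laboratory summaries, for which no safety hypothesis is tested, and exploratory biomarker models that the Addendum itself labels post hoc. The primary PUL endpoint uses no blood baseline. This is an inexpensive improvement to interpretation, not a threat to the trial's main conclusions.

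**What to change.** Change the analysis only; enrollment has ended, so rewording the draw rule would alter no baseline.

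1. For every baseline and post-baseline blood sample, derive a flag for whether it was drawn after that visit's premedication started. Use collection dates, with times where recorded, and the medication start dates and times captured under Protocol 12.4. Protocol 11.9 promises only the date for the named biomarkers (11.10 gives date and time for exploratory ones). Where only a date exists, let the flag mean a draw on Day 1 or on an infusion day.
2. Keep the SAP 4.2 baseline for the main summaries.
3. Add a sensitivity analysis of laboratory change from baseline and of the Addendum biomarker models that uses the flag, either as a sample-level covariate or by restricting to pairs of samples in the same state. Report how many samples carry the flag, by arm and visit.
4. Reconcile footnote 11 with the biomarker rows of Table 3, and state which applied.

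The cost is one derived variable and a little more analysis. The restricted version will have fewer subjects and wider intervals, and a date-only flag will misclassify some samples.

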8. SELECTION AND WITHDRAWAL OF SUBJECTS

Subjects who meet all inclusion criteria and no exclusion criteria will be eligible for randomization in the trial.

8.1. Subject Inclusion Criteria

Inclusion criteria will be assessed within 30 days prior to randomization unless otherwise noted:

1. Male subjects at least 10 years of age at time of consent
2. Willing and able to provide informed consent to participate in the trial if \geq 18 years of age, and assent with parental or guardian informed consent if $<$ 18 years of age
3. Diagnosis of DMD based on clinical and phenotypic manifestations consistent with DMD (e.g., family history of DMD, elevated creatine kinase, dystrophin muscle biopsy, calf pseudohypertrophy, Gowers' sign, and gait impairment before 7 years of age) with confirmatory genetic testing performed at a Clinical Laboratory Improvement Amendments (CLIA)-certified laboratory. *See exclusion criteria 4 and 5 for mutation-specific exclusions.*
4. Performance of the Upper Limb entry item score 2-5
5. If ambulatory, 10-meter walk/run velocity $<$ 1 meter/second
6. Loss of independent ambulation by 18th birthday (standing unassisted or ability to take, at most, several steps independently is not considered ambulation)
7. Receiving standard of care therapy at an experienced, multidisciplinary, DMD center as evidenced by regular cardiac and pulmonary monitoring, systemic glucocorticoid treatment, and at-home range of motion exercises
8. Treatment with a systemic glucocorticoid is required for at least 12 months prior to randomization. The dose must remain stable for at least 6 months prior to randomization with the exception of either weight-based dose adjustment or a decrease in steroid dose of \leq 10% for toxicity. For patients on chronic deflazacort, treatment with an equivalent dose of prednisone or prednisolone for a period of \leq 30 days to bridge lack of availability of deflazacort during the 6 months prior to randomization is acceptable
9. Current and up-to-date immunizations according to children and adolescent Centers for Disease Control immunization schedule, unless contraindicated, including the following: meningococcal and meningococcal B; tetanus, diphtheria & acellular pertussis (Tdap); and pneumococcal polysaccharide vaccinations
10. Adequate venous access for parenteral IP infusions and routine blood collections in the judgement of the Investigator
11. Assessed by the Investigator as willing and able to comply with the requirements of the trial

8.2. Subject Exclusion Criteria

Exclusion criteria will be assessed within 30 days prior to randomization unless otherwise indicated:

1. Left ventricular ejection fraction (LVEF) < 35%
2. Elbow-flexion contractures > 30° in both extremities
3. Body mass index (BMI) > 45
4. Documentation of exon 44 skip-amenable mutation(s) in the dystrophin gene (*see Appendix 1 for comprehensive list of mutations*)
5. Documentation of dystrophin deletion mutation(s) encompassing and limited to exons 3-7
6. Percent predicted FVC (FVC%p) < 35%
7. Inability to perform consistent FVC measurement within ±15% during paired testing at screening
8. Risk of near-term respiratory decompensation in the judgment of the investigator, *or* the need for initiation of non-invasive ventilator support as defined by serum bicarbonate ≥ 29 mmol/L at screening
9. History of non DMD-related chronic respiratory disease requiring ongoing or intermittent treatment, including, but not limited to, asthma, bronchitis, and tuberculosis
10. Acute respiratory illness within 30 days prior to screening
11. Initiation of non-invasive ventilation within 30 days prior to screening, or the anticipated need to initiate non-invasive ventilation within the 12 months following screening
12. Planned or anticipated thoracic or spinal surgery within the 12 months following randomization
13. Planned or anticipated lower extremity surgery within the 12 months following randomization, if ambulatory
14. Known hypersensitivity to dimethyl sulfoxide (DMSO) or bovine products
15. Initiation of treatment with metformin or insulin within 3 months prior to randomization
16. Initiation of treatment with an FDA-approved exon skipping therapy for the treatment of DMD within 24 months prior to randomization or dose adjustments to the therapy within 12 months prior to randomization with the exception of weight-based dose adjustments.
17. Treatment with human growth hormone (HGH) within 3 months prior to randomization, unless on a stable dose (as determined by the site PI) for at least 24 months prior to randomization
18. Treatment with idebenone within 3 months prior to randomization
19. Treatment with a cell therapy product within 12 months prior to randomization
20. Treatment with an investigational product within 6 months prior to randomization

21. History, or current use, of drugs or alcohol that could impair their ability to comply with participation in the trial
22. Inability to comply with the investigational plan and follow-up visit schedule for any reason, in the judgment of the investigator

8.3. Screen Failures

Any subject who provides written informed consent/assent and is ultimately not randomized for whatever reason will be classified as a screen failure. All subjects, including screen failures, must be accounted for in the clinical database.

Screen failures may be re-screened at the discretion of the Investigator using the originally assigned screening number.

8.4. Subject Withdrawal Criteria

Every effort will be made to have each randomized subject complete all elements of the trial. If a subject has started at least one IP infusion and withdraws prior to trial completion, all attempts must be made to perform the trial assessments indicated for the Month 12 visit (i.e., final comprehensive visit).

[figure not shown]
[figure not shown]
Criteria for withdrawal from trial participation include the following reasons:

- A subject may withdraw his consent at any time without prejudice to his care.
- At the discretion of the Investigator, the subject may be withdrawn from the trial for lack of adherence to the investigational plan.
- A subject may be withdrawn from the trial for an acute reaction to IP or other safety issue that prevents repeat infusions. In this instance, the subject should be followed on schedule until completion of assessments through the Month 12 visit or for at least 3 months post last IP infusion and then complete a final comprehensive visit.

[figure not shown]
